Appendix: Patient Survey for ADAPTOR Participants

Aspirin Trial Questions

https://docs.google.com/forms/d/lha6FWkw7GH2oJdvdow...

Α	spirin Trial Questions
	The Health eHeart Alliance
Ha	ve you had a history of MI (myocardial infarction?)
0	Yes
0	No
0	Don't know
	ve you had a history of CAD (Coronary artery disease?) Yes
0	No
0	Don't know
	you take any of these medications on a regular basis? rk all that apply
	Aspirin 81mg "baby aspirin"
	Aspirin 325mg "regular aspirin"
	Aspirin at another dose
	Apixaban (Eliquis)
	Clopidogrel (Plavix)
	Dabigatran (Pradaxa)
	Prasugrel (Effient)
	Rivaroxaban (Xarelto)
$\overline{}$	Ticagrelor (Brilinta)

1 of 3 2/3/15, 12:39 PM

Aspirin Trial Questions

https://docs.google.com/forms/d/lha6FWkw7GH2oJdvdow...

Answer only if applicable	
If you take Aspirin: How ofter	n do you usually take it?
Answer only if applicable	
 Every day, 2 times per day 	
 Every day, 1 time per day 	
 Every other day 	
Less often	
Have you ever had to stop tal or bleeding?	king aspirin because of side effects like a rash, upset stomaci
Answer only if applicable	
O Yes	
O No	
-	aking aspirin please list them
If you had side effects from t Answer only if applicable	aking aspirin please list them
Mould you be willing to be a participating in the study's data	patient advisor to this study? study design, identifying ways to recruit study participants, helping ent form, helping identify study outcomes important to patients, safety monitoring process and helping interpret and disseminate
Mould you be willing to be a participating in the study's data results.	patient advisor to this study? study design, identifying ways to recruit study participants, helping ent form, helping identify study outcomes important to patients,
Would you be willing to be a participating in the study's data results. Yes	patient advisor to this study? study design, identifying ways to recruit study participants, helping ent form, helping identify study outcomes important to patients,
Answer only if applicable Would you be willing to be a particular to be a partient friendly conse	patient advisor to this study? study design, identifying ways to recruit study participants, helping ent form, helping identify study outcomes important to patients,

2 of 3 2/3/15, 12:39 PM

References

- 1. Heart Disease Facts: America's Heart Disease Burden. Centers for Disease Control and Prevention, 2014. (Accessed February 5, 2015, at http://www.cdc.gov/heartdisease/facts.htm.)

Statistical Analysis Plan

Aspirin Dosing: A Patient-Centric Trial Assessing Benefits and Long-Term Effectiveness **"ADAPTABLE"**

Protocol History

Version 1.0	May 1, 2020
Version 1.1	December 7, 2020
Version 1.2	February 9, 2021

Prepared by

[name], MS Biostatistician III Duke Clinical Research Institute

[name] Director, Center for Predictive Medicine Duke Clinical Research Institute

[name] Professor of Biostatistics Duke Clinical Research Institute

1	Sy	nopsis	
2	Stu	udy Aims	
	2.1	.1 Aim 1	
	2.1	.2 Aim 2	
	2.1	.3 Aim 3	
3	Da	ta Sources	
4	Ra	ndomization and Drug Allocation	4
5	Stu	udy Endpoints	5
	5.1	Primary Endpoint	
	5.2	Secondary Endpoints	
	5.3	Primary Safety Endpoint	
6	lde	entification of Endpoints	5
7	Su	mmary of Statistical Methods	6
	7.1	Baseline Demographics and Medical History	6
	7.2	Populations for Analysis	7
	7.3	Primary Effectiveness Comparison	7
	7.4	Primary Safety Comparison	
	7.5	Censoring Rules	
	7.6	Power	
	7.7	Secondary Endpoints	9
	7.8	Prior Treatment Effect	
	7.9	Handling of Missing Data	
	7.9	.1 Outcome Dates	
	7.9	.2 Event-free Survival Outcomes	11
	7.9	.3 Longitudinal Outcome Data	11
	7.10	Planned Sensitivity Analyses	11
	7.11	Subgroup Analyses (Heterogeneity of Treatment Effect)	
8	Та	bles and Figures	
9	Re	ferences	

1 Synopsis

To identify the optimal dose of aspirin for secondary prevention in patients with atherosclerotic cardiovascular disease (ASCVD), we conducted a pragmatic clinical trial in which 15,000 patients who are at high risk for ischemic events were randomly assigned in a 1:1 ratio to receive an aspirin dose of 81 mg/day vs. 325 mg/day. Study participants were enrolled over 38 months. Maximum follow-up was 50 months (extended from originally specified 44 months). The primary endpoint is a composite of all-cause death, hospitalization for MI, or hospitalization for stroke. The primary safety endpoint is hospitalization for major bleeding with an associated blood product transfusion.

Additional details about the inclusion and exclusion criterion are contained in the study protocol. Many of the following details are also contained in the study protocol, with some differences in proposed statistical methodology.

2 Study Aims

The major aims of the trial are to test the effect of an aspirin policy on efficacy and safety outcomes, as well as to identify if events captured through electronic health record (EHR) data can be used appropriately in future trials. More specifically, the aims are as follows:

2.1.1 Aim 1

To compare the effectiveness of two daily doses of aspirin (81 mg and 325 mg) in reducing a composite endpoint of all-cause death, hospitalization for nonfatal MI, or hospitalization for nonfatal stroke in high-risk ASCVD patients. Secondary endpoints will be the components of the composite primary endpoint as well as coronary revascularization procedures (percutaneous coronary intervention [PCI] or coronary artery bypass grafting [CABG]) performed during study follow-up. The primary safety endpoint will be hospitalization for major bleeding complications with an associated blood product transfusion.

2.1.2 Aim 2

To compare the effects of aspirin in selected, pre-specified subgroups of patients, including women vs men, older vs younger patients, racial minority patients vs white patients, patients with vs. without diabetes mellitus, patients with vs. without chronic kidney disease (CKD), and patients with vs. without treatment with a concomitant P2Y12 inhibitor at baseline.

2.1.3 Aim 3

To develop, refine, and evaluate the infrastructure for PCORnet to conduct multiple comparativeeffectiveness trials in the future. This aim will be accomplished with a "phased-in" approach that will allow for an initial testing of the PCORnet infrastructure followed by adjustments to the trial operational plan to most efficiently accomplish Aims 1 and 2. Also, we will carefully monitor the recruitment and enrollment patterns within and across participating Clinical Data Research Networks (CDRNs) and a Health Plan Research Network (HPRN) and will provide regular feedback reports to each CDRN and HPRN to promote consistent recruitment practices.

Note that the statistical analysis plan for Aim 3 will be described in a separate document.

3 Data Sources

Data sources include the following: electronic health record (EHR) data organized according to the PCORnet Common Data Model (CDM) format, Medicare claims data (CMS), private health insurance claims and patient reported outcomes (PRO) and patient reported data collected via the study web portal. Patient portal data was collected on a continual basis via the web portal.

CDM data was extracted through queries issued by the DCRI data coordinating center for a prespecified number of times throughout and at the end of the trial. Claims data were collected periodically at a few specified time intervals.

4 Randomization and Drug Allocation

Patients were randomized via a patient portal in a 1:1 ratio to receive 81 mg vs. 325 mg of aspirin in an open-label fashion. Patients were asked to obtain their randomized aspirin dose at their local pharmacies. The randomization scheme was established before the inception of enrollment. Randomized treatment assignment has been obtained from the patient portal data. Compliance with the randomized aspirin dose assignment has been obtained from patient reported data.

Additionally, patients have been randomly assigned to follow-up intervals of every 3 vs 6 months. By embedding a secondary randomization for follow-up time intervals, the best methods for optimizing participant adherence, compliance, and retention in this pragmatic trial will be investigated.

5 Study Endpoints

5.1 Primary Endpoint

The primary endpoint of this study is the composite rate of all-cause mortality, hospitalization for nonfatal MI, or hospitalization for nonfatal stroke. Traditional reporting of potential endpoints by study sites with independent adjudication by a Clinical Events Committee has not been done in this trial given the pragmatic nature of the ADAPTABLE study.

We have conducted an endpoint validation plan to ensure the accuracy of the current endpoint classification methodology when compared with clinical endpoint adjudication processes used in traditional clinical trials. See *ADAPTABLE Validation Plan* for the description of the validation plan, as it has been approved by PCORI. Validation will be summarized in the final report as a separate topic and will not be part of the main trial SAP. The results of the validation will not be incorporated into the primary analyses.

5.2 Secondary Endpoints

[figure not shown]
Secondary endpoints include the components of the primary endpoint, coronary revascularization procedures (PCI and CABG), and quality of life and functional status.

5.3 Primary Safety Endpoint

The primary safety endpoint is hospitalization for major bleeding. Bleeding events include intracranial hemorrhage, GI bleeding, bleeding in other locations, or a control of bleeding procedure. To qualify as a major bleeding event, there also must be documented evidence of a blood product transfusion within +/- 7 days of the bleed.

6 Identification of Endpoints

The method for identification of clinical endpoints is documented in the protocol. Endpoints were identified through electronic sources (including EHR [PCORnet CDM], CMS claims or private insurance claims data) or patient reported via the patient portal (see figure below). Confirmation by electronic data is required for patient reported clinical endpoints. Some clinical endpoints, based on patient-reported events that could not be confirmed or refuted by the data sources listed above, were confirmed through medical record review.

For endpoints based on a hospitalization for a specific reason (MI, stroke, bleeding), the primary analysis will include endpoints identified by diagnostic codes both (a) in the principal position, and (b) for which the position is unknown. In the CMS and private insurance claims data, diagnostic code position for inpatient encounters is usually known, and we will use all codes reported. In the PCORnet EHR data, most, but not all, sites consistently use the principal/secondary designation for diagnoses. When diagnosis position is unavailable for a specific code, its position is recorded as "Other/Unknown" in the PCORnet CDM. Therefore, in the PCORnet data, when diagnosis position is available, only codes in the principal position will be used; but when diagnosis position is unavailable, all codes will be used. This requirement will ensure that we do not exclude events from sites that do not record this information. We will use diagnosis codes known to be (and designated as) secondary in sensitivity analyses only. More details on endpoint extraction are contained in the Query Technical Specifications.

Sensitivity analyses, including analyses addressing potential misclassification in endpoint definitions, are described in Section 7.10.

7 Summary of Statistical Methods

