Another source of bias may exist with respect to aspirin therapy prior to randomizations. We expect that most patients recruited into the ADAPTABLE trial will already be treated with long-term aspirin therapy, given the nature of the inclusion criteria and the known high utilization of aspirin for the secondary prevention of coronary artery disease in the US. However, we will add a sensitivity analysis with a 10-day landmark to the statistical analysis plan (SAP) that excludes all events occurring in the first 10 days following randomization, in order to formally test for a legacy effect of the aspirin dose taken before randomization.

III.A.4. Patient Engagement

[figure not shown]
The ADAPTABLE trial will address several key questions mentioned in PCORI's definition of patient-centered outcomes research. This trial is designed to help individuals answer the following questions: "Given my personal characteristics, conditions, and preferences, what should I expect will happen to me?" "What are my options and what are the potential benefits and harms of those options?" and "What can I do to improve the outcomes that are most important to me?"

The study seeks to make more relevant, detailed information regarding aspirin therapy as secondary prevention for ASCVD available to patients and their caregivers by answering question such as "What is the most effective dose of aspirin in secondary prevention of ASCVD?" and "What are the bleeding risks associated with taking 81 mg or 325 mg of aspirin?" Of the 40 topics suggested for the first PCORnet study, 6 were selected for consideration through the PCORI Advisory Panel Prioritization process by a body consisting of patients, scientists, and other stakeholders charged with prioritizing CER topics for PCORI. ADAPTABLE was chosen to be the first PCORnet study based on its importance to patients, clinicians, and scientific communities.

Patient and stakeholder engagement has been a priority to the study team since the inception of ADAPTABLE. A partnership was formed with the Health eHeart Alliance Patient-Powered Research Network to support ADAPTABLE by leading the CDRN patient representative team called the Adaptors. Additionally, 2 seasoned cardiology patient advocates served on the protocol design committee to assist

with defining essential characteristics of the study, participants, and outcomes. These advocates also worked actively with the study team and Health eHeart to develop the patient-engagement plan.

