Because this is an open-label trial in which participants and their healthcare providers will know their randomized dose of aspirin, the CDRN will be asked to engage regularly with the healthcare providers in their network regarding the rationale for the trial and the importance of compliance with the randomized treatment assignment to minimize patient cross-over. These clinical engagement approaches will be designed to facilitate discussions with healthcare providers who will be asked not to change a participant's aspirin dose during the trial unless it is absolutely necessary to ensure participant safety. On the ADAPTABLE participant portal, participant will be reminded of the importance of adhering to the aspirin dose they were randomly assigned to unless their physician changes their dose for a major safety concern. Participant who cross over will be analyzed as they were originally randomized according to the intention-to-treat (ITT) principle.

III.C.5.b. Drug Discontinuation – Monitoring and Recommendations

Aspirin use will be collected via the responses to the participant questions during follow-up. During each follow-up contact, compliance with the randomized aspirin dose will be assessed. The occurrence of and reasons for discontinuing aspirin or changing the dose of aspirin will be ascertained. In the event of aspirin intolerance or bleeding, the decision to continue the randomized aspirin dose, convert to a lower or higher aspirin dose, or to discontinue aspirin therapy will be left to the treating physician's discretion. Participants who discontinue aspirin therapy altogether will remain in the trial for clinical outcomes follow-up according to the ITT principle.

If a female participant becomes pregnant or plans to attempt to become pregnant during study follow-up, then aspirin should be permanently discontinued. Furthermore, if a participant requires an oral anticoagulant during study follow-up, the treating physician should carefully consider whether to continue aspirin based upon the estimated bleeding risks of aspirin used together with an oral anticoagulant, based on the clinical context. Finally, participants who develop an intracranial hemorrhage or a life-threatening bleeding event during study follow-up should be considered for permanent discontinuation of aspirin, at the discretion of their treating physician.

III.C.5.c. Delinquent or Missing Follow-up

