This endpoint includes death from any cause (all-cause mortality).

III.E.4.b. Hospitalization for Nonfatal MI

The endpoint of hospitalization for nonfatal MI will be ascertained using ICD-10-CM diagnosis codes (to be listed in the SAP) associated with an encounter in a hospital setting. Priority will be given to diagnosis codes in the principal or primary position. Diagnosis codes in secondary or unknown positions also will be searched for the identification of potential endpoints. The extent to which events identified by diagnosis codes in secondary or unknown positions will or will not be used in the final analysis will be detailed in the SAP. The MI coding algorithm that will guide these efforts was validated for use in FDA's Mini-Sentinel program⁹² and has been shown to have a positive predictive value (PPV) of 86%. 93

III.E.4.c Hospitalization for Stroke

The endpoints of hospitalization for hemorrhagic stroke or ischemic stroke will be ascertained using ICD-10-CM diagnosis codes (to be listed in the SAP) associated with an encounter in a hospital setting. Priority will be given to diagnosis codes in the principal or primary position. Diagnosis codes in secondary or unknown positions also will be searched for the identification of potential endpoints. The extent to which events identified by diagnosis codes in secondary or unknown positions will or will not be used in the final analysis will be detailed in the SAP. The stroke coding algorithm that will guide these efforts has been shown to have a PPV 85% or greater. Is chemic stroke hospitalizations and hemorrhagic stroke hospitalizations will be incorporated into a combined endpoint of all stroke events.

III.E.4.d. Coronary Revascularization

Coronary revascularization includes all coronary revascularization procedures (PCI/CABG) performed during the study. These will be identified using ICD-10-PCS procedure codes and CPT procedure codes (to be listed in the SAP).

III.E.4.e. Hospitalization for Major Bleeding

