The endpoints of hospitalization for intracranial bleeding, GI bleeding, and bleeding at another location will be ascertained using ICD-10-CM diagnosis codes (to be listed in the SAP) in a hospital setting. Priority will be given to diagnosis codes in the principal or primary position. Diagnosis codes in secondary or unknown positions also will be searched for the identification of potential endpoints. The extent to which events identified by diagnosis codes in secondary or unknown positions will or will not be used in the final analysis will be detailed in the SAP. The bleeding coding algorithm that will guide these efforts has been shown to have a PPV of 92%. Additionally, procedure codes will be searched for control of bleeding and blood product transfusions and may be used in combination with the diagnosis codes for the definition of the composite major bleeding outcome.

III.E.4.f. Quality of Life and Functional Status

In addition to the effectiveness and safety endpoints listed above, we will collect data on quality of life and functional status as shown in **Table 5**:

Table 5. PCORI Pat	ient-Reported Outcomes Common Measures -	– Core and Recommended (LOINC Panel 75418-4)
Domain	Item text	Answer list
General Health	In general, would you say your health is	5=Excellent; 4=Very good; 3=Good; 2=Fair; 1=Poor
Quality of life	In general, would you say your quality of life is	5=Excellent; 4=Very good; 3=Good; 2=Fair; 1=Poor
Physical Function	Are you able to run errands and shop?	5=Without any difficulty; 4=With a little difficulty; 3=With some difficulty; 2=With much difficulty; 1=Unable to do
Depression	In the past 7 daysI felt depressed	1=Never; 2=Rarely; 3=Sometimes; 4=Often; 5=Always
Fatigue	During the past 7 daysI feel fatigued	1=Not at all; 2=A little bit; 3=Somewhat; 4=Quite a bit; 5=Very much
Sleep Disturbance	In the past 7 daysI had a problem with my sleep	1=Not at all; 2=A little bit; 3=Somewhat; 4=Quite a bit; 5=Very much
Social Roles & Activities	I have trouble doing all of my regular leisure activities with others	5=Never; 4=Rarely; 3=Sometimes; 2=Usually; 1=Always

III.E.5. Events Collection

(Refer to Section III.A.5.d. Identifying Endpoints.)

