7.4 Primary Safety Comparison

The primary safety endpoint of this study will be the first occurrence of hospitalization for major bleeding. The primary safety analysis will be performed by the ITT principle based on randomized treatment assignment. Cumulative endpoint event rates will be estimated using Kalbfleisch & Prentice's nonparametric estimator of the CIF, taking into account the competing risk of all-cause death. Event-free survival rates will be compared using the Fine and Gray method, equivalent to the Cox proportional-hazards model when competing risks are present, using censoring rules defined in Section 7.5. Grey's test is the competing risk equivalent to the log-rank test for comparing the equality of event curves. The test will be two-tailed and will be performed at an overall α of 0.05.

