7.7 Secondary Endpoints

Secondary endpoints include:

- All cause death
- Hospitalization for nonfatal MI
- Hospitalization for nonfatal stroke
- Coronary revascularization (PCI or CABG)
- Quality of life and functional status components include:
 - o Current Health
 - Physical function
 - Depression
 - Fatigue
 - Sleep disturbance
 - Social roles and activities
 - Pain Interference

Patient reported coronary revascularization events that do not match to one of the electronic sources will not be further verified. As such, these PROs will not be counted as events in the secondary event analyses.

All-cause death will be analyzed using a Cox proportional hazards model. All other time-to-event outcomes will be analyzed using the Fine and Gray method, equivalent to the Cox proportional-hazards model when competing risks are present, with all-cause death as the competing risk. The test will be two-tailed and will be performed at an overall α of 0.05. The proportional hazards assumption will be checked for randomized treatment arm using weighted Schoenfeld residuals. If there is evidence of non-proportionality, a cautious interpretation of the model hazard ratio will be encouraged, and non-parametric event rate estimates will be emphasized, as described for the primary effectiveness analysis.

Quality of life and functional status data are collected on numerical scales (1:excellent health-5:worst health). They will be analyzed as continuous variables. Mixed models using restricted maximum likelihood estimation (REML) will be employed to model trajectory of measures over time by treatment group. Mixed models account for the correlation structure imposed by repeated measures within participants while using all available data, from baseline to the end of the study, regardless of exact follow-up time. The intercept and slope will be modeled as random effects. The covariance structure for random effects will be modeled using an unstructured form. Time from baseline measurement and randomized treatment arm will be included in the model as fixed effect. Time will be tested for linearity using natural cubic splines. An interaction between randomized treatment arm and time will be assessed, as will the overall effect of randomized treatment arm.

Since these measures are discrete scores, it is expected that normality assumptions will not hold. Natural log and other appropriate transformations will be considered, as well as several distributions and link functions.

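### An intracranial bleed that is nonfatal and not transfused enters no stated safety result; a descriptive by-arm summary would close the gap cheaply

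*SAP*

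**What the plan says.** SAP 5.3 defines the bleeding types: "Bleeding events include intracranial hemorrhage, GI bleeding, bleeding in other locations, or a control of bleeding procedure". It then adds the transfusion condition, "there also must be documented evidence of a blood product transfusion within +/- 7 days of the bleed", with no exception for intracranial bleeding. SAP 7.4 states what is compared: "The primary safety endpoint of this study will be the first occurrence of hospitalization for major bleeding". That is one time-to-first-event comparison across all sites, with death as a competing risk.

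Protocol III.E.4.c handles the other route by which an intracranial bleed can be counted: ischemic and "hemorrhagic stroke hospitalizations will be incorporated into a combined endpoint of all stroke events". Pooled stroke feeds the primary composite and the secondary endpoint listed in SAP 7.7 as "Hospitalization for nonfatal stroke". Neither SAP 5.2 nor SAP 7.7 lists intracranial hemorrhage, hemorrhagic stroke or any bleed site as an endpoint.

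The data are nevertheless to be collected. Protocol III.E.4.e says: "The endpoints of hospitalization for intracranial bleeding, GI bleeding, and bleeding at another location will be ascertained using ICD-10-CM diagnosis codes". Protocol III.C.5.b gives this bleed special weight, with no transfusion condition: "participants who develop an intracranial hemorrhage or a life-threatening bleeding event during study follow-up should be considered for permanent discontinuation of aspirin", at the treating physician's discretion. Protocol III.A.4 names, among the questions the study seeks to answer for patients: "What are the bleeding risks associated with taking 81 mg or 325 mg of aspirin".

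**The concern.** A transfusion requirement works as a severity threshold when severity shows itself as blood loss. An intracranial bleed can be grave without any transfusion, so the rule may sort these cases by something other than their seriousness. A nonfatal case without transfusion then either counts as a stroke, mixed with ischemic strokes, or is not counted at all.

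What is at stake is the benefit-risk account of the two doses. If one dose caused more of these bleeds, the stated safety comparison would not show the non-transfused nonfatal ones. Pooled stroke could also hide the difference if ischemic stroke moved the other way. A split chosen after the data are seen would carry less weight than one named beforehand.

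**Working it through.** **Where each case goes under the stated rules.** Assume a hospitalization whose code is in a position that counts. Transfused means a documented blood product transfusion within 7 days either side.

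| Intracranial bleed | Stated safety result | Stated effectiveness result |
|---|---|---|
| Nonfatal, transfused, in stroke code list | Major bleeding, if the first | Pooled stroke |
| Nonfatal, transfused, not in stroke list | Major bleeding, if the first | None |
| Nonfatal, not transfused, in stroke list | None | Pooled stroke |
| Nonfatal, not transfused, not in stroke list | None | None |
| Fatal | Major bleeding only if transfused; otherwise death as competing event | Death |

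Rows three and four are the gap. Whether row four has any members depends on code lists that are not in the supplied text.

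**Whether another stated analysis fills it.** The 10-day landmark (SAP 7.8) only drops early events. The sensitivity analyses in SAP 7.10 address adherence, COVID-19, a Bayesian model, under-reporting and misclassification. The code-position variants there concern the primary endpoint definitions and leave the transfusion rule in place. SAP 7.11 splits by patient characteristics, not bleed site. Protocol III.E.5 says the data go to the monitoring board but states no comparison by bleed site.

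**The plan's own safety figure.** SAP 7.6 gives 81% power with 642 events for a 20% reduction, at 2.5% per year, with 38 months of accrual and 44 months maximum follow-up. The Schoenfeld formula gives Φ(|ln 0.80| × √642 / 2 − 1.96) = Φ(0.867) = 0.807. Exponential hazards of 0.025 and 0.020, uniform accrual and 5% annual loss give 642.6 events. Both agree with the SAP. The concern is about the definition, not this calculation.

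**Patient-years.** The tables do not agree on exposure, so a range is carried:
- Protocol Table 7 (2%, 25% reduction): 436 / ((0.020 + 0.015) / 2) = 436 / 0.0175 = 24,914.
- Protocol Table 6 (overall rate 4.2%, relative risk 0.85): 1322 / 0.042 = 31,476.
- The exponential model above, run to 50 months: 34,898.

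**Expected intracranial bleeds, both arms.**
- Protocol II.D.2 and IV.A.2 put the risk below 0.04% per year: 24,914 × 0.0004 = 10.0 and 34,898 × 0.0004 = 14.0. These are ceilings.
- Protocol Table 3 reports 0.49% of aspirin patients ever having one, with no duration. If that accrued over 1 to 3 years (an assumption), the rate is 0.49% / 3 = 0.163% to 0.49% per year: 24,914 × 0.00163 = 40.7, up to 34,898 × 0.0049 = 171.0. Table 3 counts reports, not hospitalizations.

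**Precision.** The 95% interval is exp(ln 1.5 ± 1.96 × √(4/n)), with a hazard ratio of 1.5 assumed for illustration:
- n = 10: 0.43 to 5.2.
- n = 13 (31,476 × 0.0004 = 12.6): 0.51 to 4.45.
- n = 14: 0.53 to 4.3.

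Power to detect 1.5 with 13 events is Φ(ln 1.5 / √(4/13) − 1.96) = 0.11.

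**The case against.** The strongest reply is that most of this harm is already compared by dose. Fatal cases enter all-cause death, transfused cases enter major bleeding, and nonfatal hemorrhagic stroke enters the primary composite and the stroke endpoint. Charging a hemorrhagic stroke against a dose in a net-effect composite is a legitimate choice. This stands, and it is why the gap is confined to the safety results.

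Several stronger readings are tempting but unsupported:
- *A dose difference has nowhere prespecified to appear.* Pooled stroke and death are prespecified places. SAP 8 also refers to table shells that are not in the file and could break bleeding down by site.
- *Non-transfused bleeds count in no endpoint.* That is so only for codes outside the stroke list, and neither list can be seen.
- *The protocol promises patients the intracranial risk of each dose.* Protocol III.A.4 gives bleeding risk as an example of a question the study seeks to answer, and the major bleeding comparison partly answers it. Protocol III.C.5.b is management guidance, not an endpoint definition.
- *The SAP slipped the transfusion rule in.* Protocol III.E.4.e only says transfusion codes may be used, but Protocol I.A, I.B and III.E.3 already tie the endpoint to transfusion. It is a deliberate threshold.

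It is also fair that about 10 to 14 events settle little, and that SAP 7.7 makes no multiplicity adjustment, so a sparse hazard ratio could be over-read. This argues against a test, not against showing the events by arm.

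**Conclusion.** The point holds as a low-cost improvement. In the supplied protocol and SAP text, intracranial hemorrhage reaches a safety result only if transfused within the window, and then only inside a pooled first-bleed endpoint. The nonfatal, non-transfused case is in no stated safety result. This follows from the definitions and does not depend on any assumed number.

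The size is uncertain. At the protocol's only annual rate, which is a ceiling, there would be about 10 to 14 intracranial bleeds in all. Table 3 would imply roughly 40 to 170, but only under an assumed 1 to 3 years of accrual. The documents do not give the share transfused, so the number falling outside the safety endpoint cannot be stated. A reader might infer that the primary, stroke or major bleeding conclusion is therefore wrong; nothing here shows that. If the table shells already carry this row, SAP 7.4 need only refer to it.

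**What to change.** Keep every existing endpoint and the transfusion rule. Add to SAP 7.4 a prespecified descriptive safety summary by randomized arm of hospitalization for any intracranial hemorrhage, including hemorrhagic stroke, regardless of transfusion. Report:
- counts;
- cumulative incidence with 95% confidence interval, death as competing risk;
- a hazard ratio with 95% confidence interval, labelled as not a powered test.

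Place it beside the major bleeding result. A row for ischemic stroke alone is optional; it would show whether pooled stroke hides effects in opposite directions.

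The cost is a short paragraph and one or two output rows. Protocol III.E.4.c and III.E.4.e already call for the codes to be searched, and SAP 7.4 already specifies the methods. No alpha is spent and no new data are needed. The drawback is a sparse estimate with a wide interval, so the text should say that it can neither establish nor exclude a dose difference.
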